14.1.3 Other Specific Considerations

Adjustment for Baseline Covariates

There is no plan to make adjustment for Baseline covariates for the primary objective.

Handling Missing Data

Missing data are a potential source of bias when analyzing study data. A rigorous study design and execution will help prevent the incidence of missing data from occurring.

The primary analysis of the primary and secondary objectives will include subjects who maintain morphine monotherapy and provide data (per-protocol population). Sensitivity analyses will be performed for the primary and secondary objectives using the Multiple Imputation (MI) methodology for missing data in VAS and NOSE scores for all implanted subjects. Details of the imputation method are described in Sections 14.4.1 and 14.4.2.

Adjustment for Multiple Endpoints

As there is no hypothesis testing for the primary objective, adjustment for multiple endpoints is not required.

Interim Analysis

There is no planned interim analysis for the primary and secondary objectives in this study.

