7.1.3 Analysis Sets

Full Analysis Set

All enrolled subjects will be included in the Full Analysis Set. This data set is also used for safety analysis, as well as for the analysis of systemic opioids weaning and holiday process.

IT Trial Analysis Set

All subjects who experience the IT trial will be included in the IT Trial Analysis Set.

Implanted Analysis Set

All subjects who are implanted with the Intrathecal Drug Delivery System (IDDS) will be included in the Implanted Analysis Set. This data set is used for supporting analysis for the primary and secondary objectives, as well as the analysis of adverse events that are related to device, IT drug, and procedure, and device deficiencies.

Completers Analysis Set

The implanted subjects who provide data at both the Baseline and the 6-Month Visit will be included in the Completers Analysis Set. This data set is used for supporting analysis for the primary and secondary objectives, as well as some additional measures at the 6-Month Visit. Completers Analysis Set may vary for different measures based on the subjects who provide data.

Per-protocol Analysis Set

The implanted subjects who maintain morphine monotherapy and provide data at both the Baseline and the 6-Month Visit will be included in the Per Protocol Analysis Set. This data set is used for a supporting analysis for the primary objective and the primary analyses for the secondary objectives, as well as some additional measures at the 6-Month Visit. Per-protocol Analysis Set may vary for different measures based on the subjects who provide data.

Primary Objective Analysis Set

The implanted subjects who maintain morphine monotherapy and provide data at both the Baseline and the 6-Month Visit through the date of the snapshot that will be conducted in November 2021 will be included in the Primary Objective Analysis Set. This data set is used for primary analysis for the primary objective. This analysis set may be a subset of subjects in the Per-Protocol and Completers Analysis Sets, as additional subjects may complete their 6-Month Visit following the November 2021 snapshot.

Long-term Analysis Sets

The implanted subjects who provide data at both the Baseline and the 12-Month Visit will be included in the Long-term Analysis Sets. These analysis sets include both per-protocol population (who maintain morphine monotherapy throughout the 12-Month Visit) and completers population.

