7.8 Interim Analyses

There is no planned interim analysis for the primary and secondary objective #1 for VAS in this study. The primary objective analysis will include all subjects in the Per-protocol Analysis Set who have completed their 6-Month Visit by the snapshot date in November 2021 (Primary Objective Analysis Set). Supporting analyses for the primary objective will include all subjects who complete the 6-Month Visit. Additional details are provided in Section 7.9.1.

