7.9.1.3 Analysis Methods

The proportion of subjects with Clinical Success and its exact binomial two-sided 95% confidence interval will be reported. The primary analysis method will use all the implanted subjects who maintain morphine monotherapy and provide data at both Baseline and the 6-Month Visits through the snapshot date in November 2021 (Primary Objective Analysis Set). Assuming the estimated proportion of Clinical

Success is 70%, with a sample size of 50 subjects, the exact two-sided 95% confidence interval (CI) would be 55.4-82.1%, with a confidence width of 26.7%. The widest 95% CI would be at 28.9% for an estimated proportion of Clinical Success of 50% (95% CI 35.5-64.5%).

Three sensitivity analyses will be performed: (1) the proportion of subjects with Clinical Success and its 95% CI will be reported in subjects who maintain morphine monotherapy and provide data at the Baseline and the 6-Month Visits (Per-protocol Analysis Set), (2) the proportion of subjects with Clinical Success and its 95% CI will be reported in subjects who provide data at the Baseline and the 6-Month Visits (completers), (3) the proportion of subject with Clinical Success and its 95% CI will be reported in all implanted subjects with imputation method of MI for those who have missing VAS or NOSE at the Baseline or the 6-Month Visit. Details of the imputation method are described in Sections 7.9.2.3 and 7.9.3.3.

If more than 10% of the 6-Month Visits within the Per-protocol Analysis Set are conducted remotely, an additional sensitivity analysis of the Per-protocol Analysis Set will be performed as described in Section 7.4.1.

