7.11 Changes to Planned Analysis

The main analysis for the primary objective was originally planned to be evaluated after all subjects had reached the 6-Month Visit. The primary analysis was changed to analyze all per-protocol subjects with a 6-Month Visit through the snapshot date in November 2021 (Primary Objective Analysis Set, which will be a subset of the Per-Protocol Analysis Set). The primary objective is a characterization of the clinical success rate; it is a descriptive analysis with no hypothesis testing. Therefore, this change will affect the precision around the estimated clinical success rate for the main analysis but will otherwise minimally impact the objective. Additionally, all subjects within the Per-Protocol Analysis Set who eventually complete the 6-Month Visit will be evaluated as a sensitivity analysis for the primary objective to assess the robustness of the results.

8. Validation Requirements

Statistical programming code that affects the result of the main analysis for the primary objective shall be validated using Level I validation, which is defined as the peer reviewer independently programs output and then compares the output with that generated by the original Statistical Programmer.

Statistical programming code that affects the result of the main analysis for the secondary objectives shall be validated using at least Level II validation, which is defined as the peer reviewer reviews the code, and where appropriate, performs manual calculations or simple programming checks to verify the output. The CIP deviation summary shall be validated using at least Level III validation and the high-level adverse event summary shall be validated using at least Level II validation.

In addition, the main statistical analyses that are planned for publication and have not been previously validated should be validated with at least Level II validation.

9. References

[REDACTED]
2. [REDACTED]
3. [REDACTED]
4. NOSE: Smith HS, Kirsh KL. Documentation and potential tools in long-term opioid therapy for pain. *Anesthesiol Clin.* 2007 Dec;25(4):809-23, vii.
[REDACTED]
5. [REDACTED]
6. [REDACTED]
7. [REDACTED]

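### The SAP names two primary sets for Clinical Success, and 67 implanted and 50 evaluable do not follow from 93 enrolled at the stated attrition

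*SAP*

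**What the plan says.** **Primary set for Clinical Success.** SAP 7.11 records a change of plan: "The primary analysis was changed to analyze all per-protocol subjects with a 6-Month Visit through the snapshot date in November 2021". SAP 7.9.1.3 accordingly bases the primary analysis on implanted monotherapy subjects who "provide data at both Baseline and the 6-Month Visits through the snapshot date in November 2021 (Primary Objective Analysis Set"). SAP 7.8 restricts it to subjects "who have completed their 6-Month Visit by the snapshot date in November 2021 (Primary Objective Analysis Set"). SAP 7.1.3 gives the full Per-protocol Analysis Set the other role: "This data set is used for a supporting analysis for the primary objective and the primary analyses for the secondary objectives".

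SAP 7.4 (missing data) was not changed. It says that the primary analysis of both the primary and the secondary objectives uses monotherapy subjects with data, that is, the per-protocol population, and it mentions no snapshot. Protocol 14.1.3 and 14.3 say the same.

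**Size and precision.** Protocol 14.1.1 reports 93 enrolled, intends about 67 implanted and 50 evaluable, and assumes 33% attrition before implant and 25% between implant and 6 months. SAP section 6 uses the same rates and targets but still plans about 100 enrolled. Directly after defining the snapshot-based primary analysis at 70% assumed success, SAP 7.9.1.3 states that "with a sample size of 50 subjects, the exact two-sided 95% confidence interval (CI) would be 55.4-82.1"%, a width of 26.7 points, and that the widest interval (at 50%) is 28.9 points. SAP 7.11 concedes that "this change will affect the precision around the estimated clinical success rate for the main analysis" but gives no figure.

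**The concern.** The study estimates a proportion, so the headline result consists of that estimate and its interval. Which subjects enter it should have one answer. A programmer working from SAP 7.4 or the protocol would use every per-protocol subject. One working from SAP 7.9.1.3 would stop at the snapshot, for which only a month is given.

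The snapshot set cannot be larger than the full per-protocol set, so at the same observed rate its interval is equal or wider. It also puts Clinical Success on a different set from the primary analyses of VAS and NOSE, the two measures from which it is built.

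The stated precision depends on n=50. That number came from about 100 enrolled, and enrollment closed at 93 with the attrition rates and targets left as they were. The plan therefore promises a little more precision than its own inputs deliver, and attaches that promise to the smaller of the two candidate sets.

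**Working it through.** **Inputs.** Attrition 33% then 25%, and 93 enrolled (protocol 14.1.1). About 100 enrolled (SAP section 6). Exact two-sided 95% interval at n=50 for 70% and 50% success (SAP 7.9.1.3; also protocol 14.3).

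**1. The plan's own figures reproduce.**
- Clopper-Pearson, 35/50: 55.4 to 82.1%, width 26.7.
- Clopper-Pearson, 25/50: 35.5 to 64.5%, width 28.9.
- Attrition from 100: 100 × 0.67 = 67 implanted; 67 × 0.75 = 50.25 evaluable.

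**2. The same chain from 93.**
- Implanted: 93 × (1 − 0.33) = 62.3, against about 67 stated.
- Evaluable: 62.3 × (1 − 0.25) = 46.7, about 47, against 50 stated.
- Reaching 67 implanted from 93 would need attrition of 1 − 67/93 = 28.0%, not 33%.
- Reaching 50 evaluable from 62.3 implanted would need 1 − 50/62.3 = 19.8%, not 25%.

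**3. Interval widths, in percentage points.** The documents do not give the snapshot n. The last three rows are assumed values, for illustration only.

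| n | About 70% success | About 50% success |
|---|---|---|
| 50 (stated) | 26.7 (35/50) | 28.9 (25/50) |
| 47 (from 93 enrolled) | 27.6 (33/47) | 29.9 (23/47) |
| 45 (assumed) | 28.5 (31/45) | 30.5 (22/45) |
| 40 (assumed) | 30.0 (28/40) | 32.4 (20/40) |
| 30 (assumed) | 34.7 (21/30) | 37.4 (15/30) |

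**4. Secondary Objective #1.** Its primary analysis uses the full per-protocol set, so the snapshot does not touch it. With margin 10, SD 19 and one-sided alpha 0.025, power is 95.4% at n=50 (95% stated) and 94.2% at n=47.

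**5. The analysis-set texts side by side.** Four SAP sections (7.1.3, 7.8, 7.9.1.3, 7.11) apply the cut-off. One SAP section (7.4) and two protocol sections (14.1.3, 14.3) do not. The difference from the protocol is declared in SAP 7.11; the difference from SAP 7.4 is not addressed anywhere.

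**The case against.** The sponsor has a fair answer on most of this. SAP 7.11 declares the change openly, says that it affects precision, and keeps the full per-protocol result as a sensitivity analysis. SAP 7.4 is a general section that names a type of population, and snapshot subjects belong to that type; four specific sections agree on the cut-off. The n=50 interval is worded as an assumption and is correct for n=50. About 47 is an expectation, not a ceiling: the 25% is described as conservative, actual implant counts are not given, and 67 implanted would still yield 50. Much of this stands. It limits the size of the problem, but it does not make SAP 7.4 agree with 7.9.1.3, or make 67 and 50 follow from 93.

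A reader might infer more than the documents support:

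- **A hidden interim analysis.** SAP 7.8 says "There is no planned interim analysis for the primary and secondary objective #1 for VAS in this study", and protocol 14.1.3 says "There is no planned interim analysis for the primary and secondary objectives in this study". However, SAP 7.8 discloses the snapshot in the same paragraph, enrollment is complete, and the documents tie no stopping rule, adaptation or alpha to it. This is a matter of wording.
- **An unjustified change needing an amendment.** Protocol 14.1 and SAP 7.2 send changes that do not alter a principal feature, with their justification, to the study report. The SAP version history is also partly redacted, so the lack of a reason cannot be shown.
- **A necessarily less precise headline.** Width depends on the observed rate as well as n: 36/45 gives 25.0 points, narrower than 33/47 at 27.6. The ordering holds only at equal rates.
- **A biased headline.** Nothing in the documents shows that subjects completing before and after the snapshot differ.

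**Conclusion.** Both parts hold, and both are small. The SAP names two primary sets for Clinical Success because 7.4 was not brought into line with 7.1.3, 7.8, 7.9.1.3 and 7.11. The stated 67 implanted and 50 evaluable do not follow from 93 enrolled at the stated attrition, which gives about 62 and about 47.

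The quantified cost is about one percentage point of interval width: 27.6 against 26.7 at about 70% success, and 29.9 against 28.9 at about 50%. This assumes that the planning attrition rates hold. Any further loss from the snapshot cut cannot be sized, because its n is not stated; SAP 7.1.3 says only that it may be a subset, while 7.11 says that it will be. No hypothesis is tested on this objective, so type I error is not at stake, and the full-set estimate is reported in either case. The point deserves correction because the correction is cheap and concerns the headline estimate, not because the study's conclusions are in doubt.

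**What to change.** 1. Name one primary set for Clinical Success throughout the SAP. The full Per-protocol Analysis Set is preferable: it agrees with SAP 7.4 and protocol 14.1.3 and 14.3, and with the primary VAS and NOSE analyses. The snapshot can then be reported as an early descriptive analysis with its exact date. This changes wording in SAP 7.1.3, 7.8, 7.9.1.3 and 7.11.
2. If the sponsor keeps the snapshot as primary, update SAP 7.4, fix the exact date, and show the full-set estimate beside the headline one.
3. Restate the expected numbers from 93 enrolled in SAP section 6, SAP 7.9.1.3 and protocol 14.1.1 and 14.3: about 62 implanted, about 47 evaluable, and widths of 27.6 at about 70% and 29.9 at about 50%. Mark n=50 as the target, and say that the snapshot n is no larger than the full-set n.

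No new data or analyses are needed, since both estimates are already planned. Under option 1 the definitive estimate waits for the last 6-Month Visit. The stated precision becomes slightly less favourable, and the protocol figures need an edit as well as the SAP.
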